2.0	16OCT2018	[name]	
Adding footnote to Schedule of Events in section 4.2.
 
Added visit windows in section 7.4 for mapping the unscheduled visit if scheduled visit is missing for HbA1c data.
 
Updated site pooling information in section 8.2 to detail site pooling information.
 
Added clarification for sensitivity analysis in section 16.1.2 and 16.1.4 to handle subjects who switch to their own insulin Lantus.
 
Added clarification for immunogenicity data and PK analysis in sections 16.3 and 18.6.1 for excluding immunogenicity data and PK data from database lock.
 
Added clarification on definition of baseline hypoglycemia period in section 18.6.2.

Document: \sasdata\Mylan\Insulin_glargine\SYA22825\Biostatistics\Documentation\SAP\MYL-1501D-3004_SAP_Final_2_0 clean.doc

Author: [name]

Version Number:

2.0

Version Date:

18OCT2018

Template No: CS_TP_BS016 Revision 4
Effective Date: 01Apr2016

Reference: CS_WI_BS005

TABLE OF CONTENTS

1. LIST OF ABBREVIATIONS.....	9
2. INTRODUCTION	10
3. STUDY OBJECTIVES.....	10
3.1. Other Objectives.....	10
4. STUDY DESIGN.....	11
4.1. General Description.....	11
4.2. Schedule of Events.....	12
4.3. Changes to Analysis from Protocol	14
5. PLANNED ANALYSES	14
5.1. Data Monitoring Committee (DMC).....	14
5.2. Final Analysis.....	14
6. ANALYSIS SETS	14
6.1. All Patients Screened	14
6.2. Run-in Population.....	15
6.3. All Patients Randomized Population [RND]	15
6.4. Intent-to-Treat Population [ITT]	15
6.5. Safety Population [SAF]	15
6.6. Per Protocol Population [PP]	15
7. GENERAL CONSIDERATIONS	16
7.1. Reference Start Date and Study Day	16

Document: \sasdata\Mylan\Insulin_glargine\SYA22825\Biostatistics\Documentation\SAP\MYL-1501D-3004_SAP_Final_2_0_clean.doc

Author: [name]

Version Number:

2.0

Version Date:

18OCT2018

Template No: CS_TP_BS016 Revision 4

Reference: CS_WI_BS005

Effective Date: 01Apr2016

Analysis Plan Template

7.2.	Baseline	16
7.3.	Retests, Unscheduled Visits and Early Termination Data	16
7.4.	Windowing Conventions	17
7.5.	Statistical Tests	17
7.6.	Common Calculations	18
7.7.	Software Version	18
8.	STATISTICAL CONSIDERATIONS	18
8.1.	Adjustments for Covariates and Factors to be Included in Analyses	18
8.2.	Multicenter Studies	18
8.3.	Missing data	19
8.4.	Multiple Comparisons/ Multiplicity	20
8.5.	Active-Control Studies Intended to Show Non-inferiority or Equivalence	20
8.6.	Examination of Subgroups	20
9.	OUTPUT PRESENTATIONS	21

1. LIST OF ABBREVIATIONS

AE	adverse event
ANOVA	analysis of variance
ATC	Anatomical Therapeutic Chemical (class)
BDR	blind data review
BMI	Body Mass Index
CRF	case report form
CRO	contract research organization
DMC	data monitoring committee
HLGT	High Level Group Term
HLT	High Level Term
ICH	International Conference of Harmonization
ITT	Intent-to-Treat
LOCF	Last Observation Carried Forward
MAR	missing at random
MCMC	Markov chain Monte Carlo
MedDRA	Medical Dictionary for Regulatory Activities
MI	Multiple Imputation
MMRM	mixed model for repeated measures
PP	Per Protocol
PT	Preferred Term
RND	randomized population
SAE	serious adverse event
SAF	Safety
SAP	statistical analysis plan
SE	standard error
SMBG	Self Monitored Blood Glucose
SOC	System Organ Class
TEAE	treatment emergent adverse event
T1DM	type 1 diabetes mellitus
WHO-DD	World Health Organization – Drug Dictionary (enhanced)

Document: \sasdata\Mylan\Insulin_glargine\SYA22825\Biostatistics\Documentation\SAP\MYL-1501D-3004_SAP_Final_2_0_clean.doc

Author: [name]

Version Number:

2.0

Version Date:

18OCT2018

Template No: CS_TP_BS016 Revision 4
Effective Date: 01Apr2016

Reference: CS_WI_BS005

2. INTRODUCTION

This document describes the rules and conventions to be used in the presentation and analysis of efficacy and safety data for Protocol MYL-1501D-3004. It describes the data to be summarized and analyzed, including specifics of the statistical analyses to be performed.

This statistical analysis plan (SAP) is based on [protocol amendment 1](#) (dated 11JAN2018).

3. STUDY OBJECTIVES

The primary objective is to test whether MYL-1501D product from Process VI once daily is non-inferior to MYL-1501D product from Process V once daily based on the change in HbA1c from baseline to week 18 when administered in combination with mealtime insulin lispro.

3.1. OTHER OBJECTIVES

The other objectives are to compare MYL-1501D product from Process VI and Process V at week 18, when administered in combination with mealtime insulin lispro, with respect to:

- Immunogenicity: incidence and change from baseline in the relative levels of anti-drug antibody
- Hypoglycemic events: incidence and rate per 30 days
- Occurrence of local reactions, systemic reactions and other adverse events
- Device-related safety assessment
- Change in fasting plasma glucose from baseline
- Change in insulin dose per unit body weight (U/kg) from baseline
- Change in 8-point Self-Monitored Blood Glucose (SMBG) profile from baseline

Document: \sasdata\Mylan\Insulin_glargine\SYA22825\Biostatistics\Documentation\SAP\MYL-1501D-3004_SAP_Final_2_0_clean.doc

Author: [name]

Version Number:

2.0

Version Date:

18OCT2018

[figure not shown]
Template No: CS_TP_BS016 Revision 4
Effective Date: 01Apr2016

Reference: CS_WI_BS005

Analysis Plan Template

4. STUDY DESIGN

4.1. GENERAL DESCRIPTION

This is a multicenter, double-blind, randomized, parallel-group phase 3 study in patients with type 1 diabetes mellitus (T1DM) comparing the efficacy, immunogenicity and safety of MYL-1501D products from two manufacturing processes (Process V and Process VI). A total of 202 patients with T1DM are planned to be randomized in a 1:1 ratio between MYL-1501D Process V and MYL-1501D Process VI. Approximately 110 sites will be included in the study.

After up to 2-week screening period, all patients will be titrated on Lantus® during a 4-week run-in period, and will be shifted from their current mealtime insulin to Humalog®. The patients will be randomized (stratified by investigational site and time of administration of glargine [morning and evening]); one group will receive MYL-1501D product from Process V, while the other group will receive MYL-1501D product from Process VI for 18 weeks. A follow-up visit will be scheduled 2 weeks after last dose of MYL-1501D.

The none hypothesis is that the upper bound of treatment difference (Process VI minus Process V) is over 0.4 and alternative hypothesis is that upper bound of treatment difference is less than or equal to 0.4.

Patients will remain blinded until the database is locked, then an unblinding request form will be sent to the IVR provider in order to get the randomization code. Any analyses done prior to database lock will use dummy treatments.

Document: \sasdata\Mylan\Insulin_glargine\SYA22825\Biostatistics\Documentation\SAP\MYL-1501D-3004_SAP_Final_2_0_clean.doc

Author: [name]

Version Number:

2.0

Version Date:

18OCT2018

Template No: CS_TP_BS016 Revision 4
Effective Date: 01Apr2016

Reference: CS_WI_BS005

Analysis Plan Template

4.2. SCHEDULE OF EVENTS

Study Periods	Screening	Run-in Period				Randomized Comparative Treatment Period									F-U
Study Visits ¹	V1	V2	V3	V4	V5	V6	V7	V8	V9	V10	V11	V12	V13	V14 (EOT)	V15 (FU)
Study Week	-6 to -4	-4	-3	-2	-1	0	1	2	4	6	9	12	15	18	20
Study Days	-42 to -28	-28±3	-21±3	-14±3	-7±3	0±3	7±3	14±3	28±3	42±3	70±7	84±7	112±7	126±7	140±7
Informed Consent	x														
Inclusion/Exclusion Criteria Review	x					x									
History of previous insulin usage	x														
Dilated Ophthalmoscopy / retinal photography if not done in the last 6 months	x														
Standard-of-care specifics ²	x	x	x	x	x	x	x	x	x	x	x	x	x	x	
Age, Gender, Height, Race	x														
Body Weight and BMI	x					x		x		x		x		x	
Pregnancy Test ³	x					x		x		x		x	x	x	
Medical History including concomitant illness	x														
Concomitant Medications	x	x	x	x	x	x	x	x	x	x	x	x	x	x	x
Vitals signs measurement (sitting)	x	x		x		x		x		x		x		x	
Physical examination	x					x								x	
12-lead ECG (supine)	x					x								x	
Randomization						x ⁸									
Record AEs and SAEs (including local and systemic allergic reactions) and hypoglycemic events ⁴ due to medication, disposable pen or needle		x	x	x	x	x	x	x	x	x	x	x	x	x	x
Record device safety information			x	x	x	x	x	x	x	x	x	x	x	x	

Document: \sasdata\Mylan\Insulin_glargine\SYA22825\Biostatistics\Documentation\SAP\MYL-1501D-3004_SAP_Final_2_0 clean.doc

Author: [name]

Version Number:

2.0

Version Date:

18OCT2018

Template No: CS_TP_BS016 Revision 4
Effective Date: 01Apr2016

Reference: CS_WI_BS005

Analysis Plan Template

Study Periods	Screening	Run-in Period					Randomized Comparative Treatment Period								F-U
Study Visits ¹	V1	V2	V3	V4	V5	V6	V7	V8	V9	V10	V11	V12	V13	V14 (EOT)	V15 (FU)
Study Week	-6 to -4	-4	-3	-2	-1	0	1	2	4	6	9	12	15	18	20
Study Days	-42 to -28	-28±3	-21±3	-14±3	-7±3	0±3	7±3	14±3	28±3	42±3	70±7	84±7	112±7	126±7	140±7
Fasting plasma glucose	x	x		x		x		x		x		x		x	
HbA1c Assay	x					x						x		x	
Fasting C-peptide, HIV, HBsAg, and HCVAb	x														
Sampling for hematology, blood chemistry and urinalysis ⁵	x					x								x	
Fasting lipid profile	x					x						x		x	
Sampling for immunogenicity ⁹	x					x		x		x		x		x	
Sampling for PK ⁶						x		x		x		x		x	
Review 8-point SMBG Profile performed in the week before the visit ⁷			x	x	x	x				x		x		x	
Dose review of Lantus, MYL-1501D and insulin lispro and instruction		x	x	x	x	x	x	x	x	x	x	x	x	x	
Dispense Study Medication and ancillary supplies		x				x				x		x			
Drug Accountability and Compliance				x		x		x		x		x	x	x	
Dispense subject diary		x				x				x		x			
Review subject diary				x		x				x		x		x	

1. Visits 3, 5, 7, 9 and 11 may be telephone contacts (grey columns represent telephone contacts).
2. Standard-of-care specifics includes assessment and documentation of the following - Training on self-management of diabetes, lifestyle modification measures (includes maintenance of appropriate body weight, following recommended physical activity, avoidance of smoking and following the recommended diet); and monitoring to prevent complications.
3. Serum pregnancy test for women of child bearing potential will be done during screening and randomization visit. During subsequent visits urine pregnancy test will be done. At the randomization visit, both urine and serum pregnancy tests will be done. Subject may be enrolled if the urine pregnancy test is negative.
4. Non-severe hypoglycemic events (which are not consider as SAE) occurring after the EOT visit will not be recorded at the follow-up visit.
5. A routine urine dipstick test will be performed by the site. A microscopic urinalysis will be performed by the central lab if the dipstick test result is abnormal.
6. The PK sample will be taken during the visit, preferably prior to the daily glargine dose. The timing of study drug administration from prior day should be collected along with the time of PK sample collection.

Document: \sasdata\Mylan\Insulin_glargine\SYA22825\Biostatistics\Documentation\SAP\MYL-1501D-3004_SAP_Final_2_0_clean.doc

Author: [name]

Version Number:

2.0

Version Date:

18OCT2018

Template No: CS_TP_BS016 Revision 4
Effective Date: 01Apr2016

Reference: CS_WI_BS005

Analysis Plan Template

7. The 8-point SMBG profile, measurement will be done by the subject at home on 3 days (of which 2 are consecutive days) in the week before the next visit. Evaluation will be based on the measurements after each 6 weeks; thus during randomized period it would done at Week 6, 12 and 18, while SMBG would be done on 3 days during Weeks 5, 11 and 17.

8. Prior to randomization, Investigator is required to confirm subject eligibility into the study based on the data collected during the screening period, including the labs values recorded during screening. In case subject does not meet the eligibility re-screening need to be confirmed by the Sponsor or designee.

9. During the Randomized Comparative Treatment Period, the immunogenicity samples should be drawn immediately following the PK sample, as outlined under Footnote 6.

4.3. CHANGES TO ANALYSIS FROM PROTOCOL

No changes.

5. PLANNED ANALYSES

The following analyses will be performed for this study:

- Final Analysis

5.1. DATA MONITORING COMMITTEE (DMC)

There will be no DMC or interim analysis for this study.

5.2. FINAL ANALYSIS

All final, planned analyses identified in this SAP will be performed by IQVIA Biostatistics following Sponsor Authorization of this SAP, Sponsor Authorization of Analysis Sets, Database Lock and Unblinding of Treatment.

6. ANALYSIS SETS

Agreement and authorization of patients included/ excluded from each analysis set will be conducted prior to the unblinding of the study.

6.1. ALL PATIENTS SCREENED

The all patients screened population is defined as all patients who consent for the study.

Document: \sasdata\Mylan\Insulin_glargine\SYA22825\Biostatistics\Documentation\SAP\MYL-1501D-3004_SAP_Final_2_0_clean.doc

Author: [name]

Version Number:

2.0

Version Date:

18OCT2018

Template No: CS_TP_BS016 Revision 4
Effective Date: 01Apr2016

Reference: CS_WI_BS005

6.2. RUN-IN POPULATION

The run-in population is defined as all patients who consent for the study and entered into the run-in phase. The patients in this population will be summarized under the total number of patients. Run-in failure patients will be summarized under the category of “run-in failure”.

6.3. ALL PATIENTS RANDOMIZED POPULATION [RND]

The all patient randomized (RND) population will contain all patients got randomized to study medication. The patients who discontinue the study during run-in period will not be included in the randomized population.

For analyses and displays based on RND, patients will be classified according to randomized treatment.

6.4. INTENT-TO-TREAT POPULATION [ITT]

The Intent-to-Treat (ITT) population includes all randomized patients (including patients who receive incorrect treatment, do not complete the trial or do not comply with the protocol).

The patients under the ITT population will be analyzed according to the planned treatment group.

All primary and secondary efficacy analysis will be based on the ITT population.

6.5. SAFETY POPULATION [SAF]

The safety population (SAF) will contain all patients who are randomized and take at least one dose of study drug.

The safety analysis will be conducted according to the treatment received. If there is any doubt whether a patient was treated or not, they will be assumed treated for the purpose of the analysis.

6.6. PER PROTOCOL POPULATION [PP]

The per-protocol population (PP) will contain all patients who complete week 18 and have HbA1c3 measurements as per the protocol, or have at least one post-baseline HbA1c data for patients who discontinue prematurely, and do not have major protocol deviation that impact the primary outcome. Patients who meet rescue medication criteria and take rescue medication will be excluded from the PP. The list of deviations leading to exclusion from the PP population will be identified, reviewed and documented prior to DB lock and determined in the blind data review meeting and documented in the blind data review report prior to the database lock. The subjects who are excluded from PP population and reason for exclusion will be listed.

Document: \sasdata\Mylan\Insulin_glargine\SYA22825\Biostatistics\Documentation\SAP\MYL-1501D-3004_SAP_Final_2_0_clean.doc

Author: [name]

Version Number: 2.0

Version Date:

18OCT2018

Template No: CS_TP_BS016 Revision 4
Effective Date: 01Apr2016

Reference: CS_WI_BS005

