7.1 Sample Size Determination

A total of 202 subjects with T1DM are planned to be randomized for this study and will receive either MYL-1501D Process V product or MYL-1501D Process VI product, in a 1:1 ratio.

The sample size estimation is based on assumptions for the change from baseline up to week 18 in HbA1c with either MYL-1501D product from Process V or Process VI. It is assumed, that true mean groups mean difference is 0.03 and standard deviation is equal to 0.74. To demonstrate non-inferiority margin of 0.4% using a 2-sided 95% confidence interval and a 90% power, a total of 172 subjects (86 subjects per treatment group) are required.

To account for a maximum of 15% of subjects being not eligible for the per protocol analysis, a total sample size of 202 is planned to be randomized for this study. The true treatment difference and standard deviation is based on previous study MYL-GAIA-3001.

No replacement of subject will be performed if subject discontinued prematurely from the study.

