7.4 Analysis Set Definitions

The ITT analysis set includes all randomized subjects (including subjects who receive incorrect treatment, do not complete the study or do not comply with the protocol or used prohibited medication).

The PP analysis set includes subjects who complete Week 18, and have HbA1c measurements as per the protocol, or have at least one post-baseline HbA1c data (for subjects who discontinue prematurely); and do not have protocol violations that impact the primary

outcome (as detailed in the statistical analysis plan). Subjects who meet rescue medication criteria and take rescue medication will be excluded from PP analysis set. The subjects excluded from the PP population will be identified before database lock (i.e., before unblinding the study team).

The safety analysis set includes subjects who take at least one dose of the study medication after randomization. For safety analyses, subjects will be categorized according to the treatment that they actually received.

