7.5. STATISTICAL TESTS

The default significant level will be (5%); confidence intervals will be 95% and all tests will be two-sided, unless otherwise specified in the description of the analyses.

Non-inferiority will be tested at 2.5% (one-sided) level of significance.

Document: \sasdata\Mylan\Insulin_glargine\SYA22825\Biostatistics\Documentation\SAP\MYL-1501D-3004_SAP_Final_2_0_clean.doc

Author: [name]

Version Number:

2.0

Version Date:

18OCT2018

Template No: CS_TP_BS016 Revision 4
Effective Date: 01Apr2016

Reference: CS_WI_BS005

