16.1.4. SENSITIVITY ANALYSIS OF PRIMARY EFFICACY VARIABLE

- Sensitivity to analysis set: the PP population will be used with the same MMRM model described above to establish non-inferiority. For sensitivity analysis, all non-missing HbA1c data will be used regardless if subject switched their assigned study medication.
- Sensitivity to missing data assumptions:
 - Same analysis approach as the primary analysis, but without imputing missing values. This will be analyzed based in ITT.
 - In another method, the same analysis approach as the primary analysis will be performed, but the imputed values will be corrected such that the full non-inferiority margin will be added for imputed values in Process VI group. This will be analysed based on ITT.
 - In a third sensitivity analysis, tipping-point analysis will be performed using an algorithm proposed by [Yan et al \(2009\)](#) to explore the robustness of the results with regard to a bias against the Process VI treatment arm and in favour of the Process V treatment arm. In order to quantify the bias (k), scenario 2 of the [Yan et al \(2009\)](#) algorithm will be used. Missing Week 18 values will have the value k (positive) added to the Process VI arm (worsening results) and subtracted from the Process V arm (improving results). The value for k is determined by adjusting the bias in an MNAR version of starting with a value of 0.01 and increasing it until the MNAR version of the MI method described in [Appendix 4](#) meets or surpasses the non-inferiority margin. That is the upper limit of 95% interval of treatment difference is ≥ 0.4 (p-value for test non-inferiority is ≥ 0.05). The seed and code for this process are detailed in [Appendix 4](#). The shift parameter as well as summary statistics for the MI model with the tipping point adjustment of k will be reported.
 - As a final sensitivity analysis, missing data will be imputed by using LOCF. An ANCOVA model will be used on the change from baseline in HbA1c to month 18. The model will include treatment (2 levels: MYL-1501D Process V and MYL-1501D Process VI) as fixed effect, the baseline HbA1c as covariate, and patient as random effect. The pooled sites and basal insulin dose time (morning or event) will also be included in the model as fixed effects. This will be analyzed on ITT and PP.
 - In addition, the means for each treatment and difference between treatments for missing data at Week 18 will be summarized for all sensitivity analyses.

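### The per-protocol analysis is not a clean on-treatment check: it admits HbA1c taken after stopping or switching product, including values the primary analysis sets to missing

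*SAP*

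**What the plan says.** **Who is in PP.** SAP V2.0 section 6.6 admits subjects who complete Week 18 with HbA1c measured per protocol, and also those who "have at least one post-baseline HbA1c data for patients who discontinue prematurely". Protocol V2.0 section 7.4 has the same alternative: "or have at least one post-baseline HbA1c data (for subjects who discontinue prematurely". Neither says the value must come from a period on the assigned product. Both exclude subjects who meet the rescue criterion and take rescue, and subjects whose protocol deviations affect the primary outcome. The SAP requires the deviation to be major and leaves the list to the blind data review before lock. The protocol had said the SAP would give the detail.

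**Which data PP uses.** SAP 16.1.4, first bullet, applies the primary MMRM to PP with the aim of showing non-inferiority, and continues: "all non-missing HbA1c data will be used regardless if subject switched their assigned study medication".

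**What the primary analysis does.** SAP 16.1.2 treats Week 18 HbA1c as missing, and then imputes it, for subjects who start rescue after Week 12 or who switch to their own Lantus.

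**Where off-product values come from.** Protocol 6.3.7 asks subjects who stop study drug, if they consent, to attend the remaining scheduled visits. Week 12 and Week 18 both include HbA1c.

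**Which analysis decides.** Protocol 7.2.3 and SAP 16.1.3 place the non-inferiority decision on ITT. Protocol 7.2.4 calls PP a robustness check.

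**The concern.** In a non-inferiority trial the PP analysis earns its place by showing whether the conclusion survives when subjects are compared on the product they were assigned. Subjects from both arms who leave their product and go on to the same or equivalent insulin no longer carry a Process VI versus Process V contrast. Their later HbA1c values pull the estimated difference toward zero, which is the favourable direction here.

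For subjects who switch to their own Lantus, the plan is the wrong way round: the ITT primary analysis discards the post-switch Week 18 value and the PP analysis restores it. PP is then less strict about treatment received than the analysis it is meant to check. What is at stake is the value of a concordant PP result as reassurance. The LOCF analysis is also run on PP, so it inherits the same gap.

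**Working it through.** **1. Who can contribute off-product values to PP**

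| Group | In PP? | Off-product HbA1c possible in the PP model? |
|---|---|---|
| Rescued (criterion met, rescue taken) | No (SAP 6.6) | No |
| Major deviation affecting the primary outcome | No (SAP 6.6) | No |
| Non-rescue switch, not classed as a major deviation | Yes | Yes (SAP 16.1.4) |
| Stopped study drug, attends later visits, not classed as a major deviator | Yes | Yes, at Week 12 or Week 18 |
| Stopped study drug, only on-product values | Yes | No |

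The last row does no harm: an on-product Week 12 value is informative, and a missing Week 18 value is handled under missing-at-random. Early-termination HbA1c is mapped by its actual day (SAP 7.4: Week 12 is days 76 to 91, Week 18 is days 121 to 133).

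**2. The plan's own sample size**

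Protocol 7.1 sets the margin at 0.4, the power at 90% and the interval at two-sided 95%, and assumes that the "true mean groups mean difference is 0.03 and standard deviation is equal to 0.74". SAP 7.5 gives the matching level: "Non-inferiority will be tested at 2.5% (one-sided) level of significance".

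- Normal approximation: n per arm = 2 × (1.960 + 1.282)² × 0.74² / (0.4 − 0.03)² = 84.1, so 85 per arm, 170 in total.
- Noncentral t: power is 89.99% at 85 per arm and 90.3% at 86. So 86 per arm reproduces the protocol's statement that "a total of 172 subjects (86 subjects per treatment group) are required".
- 172 / 0.85 = 202.4, against 202 planned.

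**3. Effect of off-product values on the PP test**

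Let f be the share of PP subjects in each arm whose Week 18 value carries no product difference. The documents do not give f, so every value below is an assumption. Put the true on-product difference at the margin, 0.4.

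- SE = 0.74 × √(2/86) = 0.113. With all 202 in PP (101 per arm), SE = 0.104.
- Expected PP difference = 0.4 × (1 − f).
- P(PP declares non-inferiority) = Φ(0.4f/SE − 1.96).

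| f | PP subjects of 172 (approx.) | Expected difference | False-positive rate, 86 per arm | 101 per arm |
|---|---|---|---|---|
| 0 | 0 | 0.400 | 2.5% | 2.5% |
| 1% | 2 | 0.396 | 2.7% | 2.7% |
| 2% | 3 | 0.392 | 2.9% | 3.0% |
| 5% | 9 | 0.380 | 3.7% | 3.9% |
| 10% | 17 | 0.360 | 5.4% | 5.8% |
| 15% | 26 | 0.340 | 7.7% | 8.3% |

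The table is a worst case for each f, because it assumes no residual difference off product. HbA1c lags, so a subject who stopped shortly before Week 18 still reflects mostly on-product exposure.

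**The case against.** The strongest defence is that SAP 6.6 already removes most of the problem. The only route the protocol defines for moving to Lantus while staying in the study is rescue (protocol 5.7), and rescued subjects who take it are out of PP. Any other insulin is prohibited and its use counts as a protocol deviation (protocol 5.6), so non-rescue switchers are candidates for exclusion at the blind data review. Attendance after stopping depends on consent, so off-product Week 18 values may be few.

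Much of this stands, and it limits the size of the point. It does not close the gap. Protocol 5.6 says deviation, whereas PP exclusion needs a major deviation affecting the primary outcome, and that list is not in the SAP. SAP 16.1.2 names own-Lantus switchers separately from rescued subjects, so the sponsor expects such cases. If every switcher were excluded, the switching sentence would have nothing to act on in the PP bullet.

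Three stronger readings are tempting, and the documents do not support them:

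- A reader might infer that anyone who stops early with one post-baseline HbA1c stays in PP. The rescue and deviation exclusions contradict that.
- A reader might infer that PP cannot support non-inferiority at all. At f of 1 to 2% the false-positive rate is 2.7 to 2.9% with 86 per arm, close to nominal.
- A reader might take the table as the trial's type I error. Non-inferiority is decided on ITT, where post-rescue and own-Lantus Week 18 values are set to missing. A wrong PP result alone does not produce a wrong trial conclusion.

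**Conclusion.** The point holds in limited form, and the wording should be corrected. The PP analysis mixes on-product and off-product HbA1c, and for own-Lantus switchers it is looser than the primary analysis. The bias runs toward confirming non-inferiority. Its size depends on an unreported share of PP subjects: negligible at 1 to 2%, modest at 5% (3.7%), and material at 10 to 15% (5.4 to 7.7%). These figures assume 86 per arm, SD 0.74, an on-product difference at the margin, equal shares off product in both arms and no residual difference off product. Nothing in the documents shows that the share is as high as 10 or 15%. The 15% in protocol 7.1 is the share expected to be ineligible for PP, not the share off product within it.

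**What to change.** 1. In SAP 16.1.4, restrict the PP analysis to HbA1c taken on the assigned product. Set values after discontinuation or a switch to missing, extending to PP what SAP 16.1.2 does at Week 18 for rescue and own-Lantus switches. State the same restriction in SAP 6.6 and for the LOCF run on PP.
2. Move the sentence on using all data regardless of switching to its own ITT sensitivity bullet, where it is a useful treatment-policy analysis.
3. Report, by arm, how many PP subjects have off-product HbA1c at Week 12 or Week 18, so that f is known.

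This changes SAP wording only. The cost is some PP precision, and the sample size does not already cover it: the inflation stated as "To account for a maximum of 15% of subjects being not eligible for the per protocol analysis" was used to get from 202 randomized to 86 per arm. As an upper bound on the loss, drop off-product subjects altogether and use power = Φ(0.37/SE − 1.96), which is 90.6% at 86 per arm:

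- 5% off product leaves about 82 per arm: SE = 0.74 × √(2/82) = 0.116, power about 89%.
- 15% off product leaves about 73 per arm: SE = 0.122, power about 86%.

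The actual loss is smaller, because on-product Week 12 values stay in the model. Requiring an on-product Week 18 value for PP membership would also remove the dilution, but it makes PP a completers analysis with its own post-randomization selection. Setting off-product values to missing is the better trade.
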